9.4.4 SAFETY ANALYSES

N/A

9.4.5 BASELINE DESCRIPTIVE STATISTICS

Study confounders and covariates (see **Section 8.1** for specific measures) will be summarized and compared at baseline. Given the small sample size, we will conduct adjusted and unadjusted analyses for variables that are statistically significantly different at baseline.

9.4.6 PLANNED INTERIM ANALYSES

Iterative refinements over three waves of implementation will be conducted by reviewing feasibility, acceptability, and fidelity measures from previous waves.

9.4.7 SUB-GROUP ANALYSES

There are not planned sub-group analyses aside from the secondary analyses described above.

9.4.8 TABULATION OF INDIVIDUAL PARTICIPANT DATA

N/A

9.4.9 EXPLORATORY ANALYSES

We will test the mediating effect of caregiver capability, opportunity, and motivation (COM-B) measures on the relationship between intervention and respiratory illness outcomes. The mediating effects will be evaluated by conducting a multi-step analysis approach. In the initial step, NB regression analyses will be conducted to examine whether there are differences in respiratory illness outcomes (number of severe respiratory illnesses, systemic steroid courses, systemic antibiotic courses, and respiratory ED visits) between the intervention and control arm, as described in the previous section. In the next step, we will conduct a sequence of univariate analyses, by regressing each potential mediator variable (caregiver capability, opportunity, and COM-B) on the binary study arm variable. If significant associations between the potential mediator variables and study arm are detected, we will regress the respiratory illness outcomes on both the mediator variables and study arm indicator variable using ANCOVA. The

mediation effect for each potential mediator variables will then be tested using the Sobel z-test based on the slope parameter estimates from the corresponding regression models.

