6.3 MEASURES TO MINIMIZE BIAS: RANDOMIZATION AND BLINDING

Random allocation will be concealed to research staff conducting recruitment and will use a 1:1 allocation with random block sizes of 2 and 4. Block randomization will be achieved with a computer-generated random number list prepared by the study biostatistician having no clinical involvement in the trial. Randomization will be stratified by site (UW vs UCLA) to account for site-specific study characteristics. After the research team member obtains participant consent, they will telephone contact the study project manager who is independent from the recruitment process to receive the group assignment. Alternatively, it may be arranged that randomization will be built into the REDCap database by the study biostatistician.

Since this study aim is feasibility, acceptability and fidelity, there is no plan for whether/when to break randomization codes. Study and clinical team members cannot practically be blinded to treatment because only those randomized to intervention will receive text messages, specific action plans, and coaching. The need for clinical team members to create action plans and interact with coaches will identify those randomized to intervention. Presumably, the need for admission to the hospital for a respiratory illness and secondary clinical endpoints (ED visits, need for antibiotics, steroids, hospital days, and death) are less prone to observer bias. The outcome evaluator (study biostatistician) will remain blinded during analyses.

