Primary Study Endpoints - Feasibility, Acceptability, Fidelity: The specific measures and pre-specified definitions of success are listed in **Section 3**. These measures will be summarized between each of the three waves with protocol adjustments made for any measures below the definition of success.

Clinical Endpoints:

- Primary clinical outcome is severe respiratory illness, defined as respiratory diagnosis requiring hospitalization. Respiratory diagnosis includes discharge diagnosis of any of the following: asthma, pneumonia

(community or hospital acquired), bronchiolitis, influenza, upper or lower respiratory tract infection, tracheitis, aspiration pneumonia/pneumonitis, chronic lung disease, respiratory failure.¹²⁰ Field-testing assessment of this endpoint with trained research personnel at study sites demonstrated inter-rater reliability (Kappa) > 0.9.

- Secondary outcomes include: total hospital days during severe respiratory illness, numbers of systemic steroid courses, systemic antibiotic courses, respiratory ED visits, and death. Systemic corticosteroid course is defined by oral or parenteral corticosteroid prescribed for respiratory diagnosis, including hydrocortisone, prednisone, prednisolone, or methylprednisolone at least 1 mg/kg/day (or 30 mg/day) x minimum 3 days, or dexamethasone at least 0.15 mg/kg/day (or 10 mg/day) x 1 or more days. Physiologic or stress replacement doses in adrenal insufficiency are excluded. Systemic antibiotic course is defined by oral or parenteral antibiotics prescribed for respiratory diagnosis x minimum 3 days. The specific antibiotics are derived from IDSA pediatric pneumonia guidelines¹²¹ and published literature.¹²² Respiratory ED visits are any ED visits not resulting in admission and have a discharge respiratory diagnosis.

Additional Assessment Measures:

MEASURES	SOURCE	MEASURE DETAIL
Covariates		
Child and Caregiver Demographics	Survey	Child: age, gender, primary language, race/ethnicity, payer, family structure Caregiver: relationship, age, gender, language, race/ethnicity, education, health literacy, ¹¹⁴ income, rurality
Confounders		
Child Clinical Characteristics	Electronic health record	Organ systems affected by chronic conditions, subspecialists in past year, medical technologies used (e.g., tracheostomy, gastrostomy, etc.), duration of enrollment clinical program, numbers of ED visits and hospitalizations in past year, and respiratory treatments at time of enrollment (medications and devices)

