Caregiver Strain	Survey	Caregiver Strain Questionnaire (CGSQ); ¹¹⁵ – mean global, objective, subjective scale scores Mental health (PHQ2) ¹¹⁶
Theory / Mechanism		
Capability	Survey	Family Caregiver Activation in Transition Measure (FCAT) ¹¹⁷ – mean composite score Caregiver General Self-Efficacy Scale (GSES) ¹¹⁸ – mean composite score
Opportunity	Survey	Family Experiences with Care Coordination (FECC) ¹¹⁹ - % top-box score for selected items
Motivation	Text logs	Confidence Responses mHealth texting (weekly score 1 through 10)

Assessment Procedures. Feasibility, acceptability and fidelity endpoint data will be collected during each of the three waves by research personnel reviewing study logs, conducting monthly chart reviews, and

administering surveys (by telephone, in person, or sending electronic self-administered links) with caregivers randomized to intervention. For active control groups participants, feasibility of assessments will be evaluated by completion rates at study exit. Caregiver and child measures above will be recorded at baseline, endpoints will be recorded at study exit (6 months after T0). Caregiving measures, which may change as a result of the intervention, will be collected at baseline and study exit. In addition, intervention and active control caregivers will be debriefed at study exit on their experiences in the study, and asked for feedback on the strengths, weaknesses and any concerns about the protocol. Between each wave and after the third wave, clinical teams at each site will be debriefed on strengths, weaknesses, and concerns about the protocol.

Reliability of Assessment Measures. The CP GMFCS measures and all the caregiving measures have been well-documented as reliable in the literature.^{11,74,115-119} We have separately established the reliability of identifying respiratory illnesses in our preliminary research (Kappa > 0.9). We will ensure reliability in data collection through direct observation, data auditing, establishing clear data dictionaries / definitions, using uniform variable definitions, and a central data repository coordinated and maintained by UW.

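### The survey-mediator models in Section 9.4.9 omit the mediator's own baseline score and any baseline severity measure, which costs power at the gate and leaves the mediator-outcome slope open to confounding

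*Combined protocol and SAP*

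**What the plan says.** Section 9.4.9 sets out the mediation analysis in steps. After the negative binomial comparison of arms, it plans "a sequence of univariate analyses, by regressing each potential mediator variable" on arm. "If significant associations between the potential mediator variables and study arm are detected", the next step is to "regress the respiratory illness outcomes on both the mediator variables and study arm indicator variable using ANCOVA". Each mediation effect is then "tested using the Sobel z-test based on the slope parameter estimates from the corresponding regression models". Neither of these two models names a baseline mediator score, site or a confounder.

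The variables exist. Section 8.1 states: "Caregiving measures, which may change as a result of the intervention, will be collected at baseline and study exit". This covers FCAT, GSES and FECC. Site is the stratification factor (Section 6.3). The Section 8.1 table lists, under the heading of confounders, child clinical characteristics that include "numbers of ED visits and hospitalizations in past year", and also caregiver strain.

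General adjustment clauses appear in Sections 4.1, 5.5, 9.3 and 9.4.5. They select variables because they differ between arms at baseline.

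**The concern.** Two separate consequences follow.

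**Power at the gate.** Arm is randomized, so the unadjusted arm effect on a mediator is unbiased. But the exit score carries between-caregiver variation that the baseline score would remove. Because a non-significant result ends the mediation analysis for that mediator, lost precision here can mean that no test is done at all.

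**The mediator-outcome slope.** Randomization does not protect this slope. If caregivers of sicker children score lower on activation or care coordination, and sicker children are admitted more, the mediator will be associated with illness without affecting it. This can happen with perfectly balanced arms, so a rule triggered by arm imbalance does not address it. Section 2.2 reports a 10-fold higher risk of respiratory hospitalization after a respiratory illness in the past year, so the severity-outcome half of the path is strong on the protocol's own account.

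At stake is the tertiary objective in Section 3: the account of how RE-PACT works that would be carried into the larger trial.

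**Working it through.** The documents give no power, effect size or correlation for the mediation analysis, so there is no stated figure to reproduce.

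**1. Gate power**

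Inputs from the documents: 90 participants at 1:1, so 45 per arm; at least 90% followed up, so 0.9 × 45 = 40.5, taken as 40 (Sections 6.3, 9.2); two-sided 0.05 (Section 9.4.1). Assumed: true arm effect d = 0.5 SD, and baseline-exit correlation r.

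Power comes from the noncentral t with noncentrality δ = d × √(n/2) / √(1 − r²). Without the baseline score, δ = 0.5 × √20 = 2.236.

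| r | 1 − r² | δ | Power |
|---|---|---|---|
| baseline not used | 1.00 | 2.236 | 60% |
| 0.3 | 0.91 | 2.344 | 64% |
| 0.5 | 0.75 | 2.582 | 72% |
| 0.7 | 0.51 | 3.131 | 87% |

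The gain reaches 5 points only when r is above about 0.35. By the normal approximation, 80% power needs 2 × (1.96 + 0.842)² / 0.5² = 62.8, so 63 per arm unadjusted. Multiplying by 1 − r² gives 47.1, so 48, at r = 0.5 and 32.0, so 33, at r = 0.7.

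**2. Mediator-outcome slope, with no true mediator effect**

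Inputs from Section 9.2: one severe illness per year, so a mean of 0.5 over six months, and overdispersion 1.0. Assumed: the links between severity, mediator and illness, with sicker children having lower-scoring caregivers. The outcome model is the linear one in Section 9.4.9.

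First simulation: 81 children, 4,000 runs, r = 0.6. The correlation is between severity and the baseline mediator (absolute value), and the rate ratio is per SD of severity.

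| Correlation | Rate ratio | Arm shift (SD) | Slope bias (events per SD) | Slope rejected | Gated Sobel positive |
|---|---|---|---|---|---|
| 0 | 1.8 | 0.5 | about 0 | 4.2% | 0.6% |
| 0.3 | 1.8 | 0.5 | −0.052 | 8.2% | 1.1% |
| 0.3 | 1.8 | 1.0 | −0.050 | 7.1% | 4.6% |
| 0.5 | 1.8 | 0.5 | −0.088 | 12.3% | 2.0% |
| 0.5 | 1.8 | 1.0 | −0.092 | 12.3% | 8.3% |
| 0.5 | 2.5 | 0.5 | −0.140 | 17.6% | 3.1% |
| 0.5 | 2.5 | 1.0 | −0.138 | 18.2% | 12.7% |

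Against a mean of 0.5 events, a bias of 0.05 to 0.14 is 10% to 28% of the mean (0.05/0.5 and 0.14/0.5).

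Second simulation: 80 children, mediator-severity correlation about −0.19 to −0.36, log-rate effect of severity 0.5 to 1.0 per SD. The slope was rejected in 7%, 12%, 15% and 29% of trials across four settings; repeat runs gave about 8-30%. Over these runs the gated Sobel test was falsely positive in about 1-6% at a 0.5 SD shift and about 5-23% at 1.0 SD.

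**3. What adjustment achieves**

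Adding severity measured without error brings slope rejection to 4-6%, but the trial will not have such a variable. It will have a past-year count. With a noisy count alone (negative binomial, mean one per year), rejection stayed at 7-17%. With the count plus the baseline mediator it fell to about 5-8%, and the slope's standard error rose by about 25%.

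**The case against.** **The planned inference is the gated Sobel test, not the slope.** This stands. At a 0.5 SD arm shift the false-positive rate for the whole procedure is about 1-6%. A reader might infer from the slope figures that the plan will often declare mediation falsely; at modest shifts the calculations do not show that. The harm there is a biased slope. Excess false positives need a larger shift.

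**The severity-mediator link is assumed.** This also stands. Section 2.2 supports a severity-outcome link, but nothing in the documents gives the size or direction of a severity-mediator link. With no link there is no bias, and if caregivers of sicker children score higher, the sign reverses. It is tempting to say that the slope is confounded; the documents support only that it is open to confounding.

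**Site may not be omitted.** Section 9.4.3 calls its main negative binomial analysis univariate and then includes site, so the same word in Section 9.4.9 need not exclude it. Nor is there any figure for a loss from omitting site; the gate gain above comes from the baseline score alone.

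**Other clauses already adjust.** Only in part. Variables that differ significantly between arms would enter an adjusted analysis under Section 9.4.5. Section 4.1 also promises control for baselines whether or not arms differ, but for the clinical outcomes, not the mediators, and Section 9.4.9 does not carry it over.

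**It is exploratory.** The pilot is declared underpowered and no decision rests on this analysis. Section 9.4.1 also refers to a detailed SAP still to be finalized, which is not among the documents reviewed and may say more. This lowers the priority but does not remove the point.

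**Conclusion.** The point holds for FCAT, GSES and FECC. The gate discards a collected baseline score, at a cost of about 4, 12 or 27 points of power at correlations of 0.3, 0.5 or 0.7 (64, 72 and 87 minus 60), given an assumed 0.5 SD effect and 40 per arm. The outcome model leaves a non-randomized slope open to confounding by a severity measure that the protocol itself lists as a confounder, and the arm-imbalance rules do not reach this. The simulated slope rejection of about 7-30% rests on assumed links that the documents do not quantify.

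A reader might extend the point to all the mediators. The documents do not support that. Motivation comes from text-message confidence, and texting is set up only in the intervention arm (Sections 1.3 and 4.2), so it has neither control-arm values nor a pre-randomization baseline to adjust for.

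Minor priority, because the objective is exploratory.

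**What to change.** In Section 9.4.9, for FCAT, GSES and FECC:

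- Replace the regression on arm alone with ANCOVA of the exit score on arm, its own baseline value and site. Site is for consistency with the other models.
- In the outcome model include arm, site, exit mediator, baseline mediator and one or two confounders fixed in advance from the Section 8.1 list, at least past-year hospitalizations. Baseline caregiver strain is a candidate for the second. About 40 expected events in 80 children (80 × 0.5) will not support a long list.
- State that the mediator-outcome slope is observational, and that this baseline adjustment does not apply to text-message confidence.

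The cost is SAP wording; no new data are needed. The analysis loses a few degrees of freedom and any caregiver with a missing baseline score, and the mediator slope has a larger standard error (about 25% in one simulation). The change brings slope rejection to about 5-8%; it reduces the confounding but does not fully remove it.

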1.2 SCHEMA

1.3 SCHEDULE OF ACTIVITIES

	STUDY PERIOD							
	Enroll- ment Visit	REPACT Intervention Period						Final Visit
Personnel involved	Research Coordina- tor	Clinicians						Research Coordina- tor
Month	0	1	2	3	4	5	6	End of Month 6
Timepoint	T ₀	T ₁	T ₂	T ₃	T ₄	T ₅	T ₆	T ₇
Confirm eligibility	X							
Informed Consent	X							
Baseline Assessment	X							
6-month Assessment								X
Randomization	X							
Subject Payment	X							X
Usual comprehensive medical care and coordination via Complex Care Program		X	X	X	X	X	X	
Intervention Arm Only								
Text Msg Training	X							
Weekly mHealth text message and response		X	X	X	X	X	X	
Intervention overview		X						
Create action plan		X						
Action planning		X	X	X	X	X	X	
JIT coaching		X	X	X	X	X	X	
Monthly study assessments		X	X	X	X	X	X	

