Tertiary/Exploratory			
To explore the mediating relationships between RE-PACT and capability, opportunity, motivation (COM-B) measures.	Capability : Family Caregiver Activation in Transition Measure (FCAT)117 – mean composite score Caregiver General Self-Efficacy Scale (GSES) 118 – mean composite score. Opportunity : Family Experiences with Care Coordination (FECC)119 - % top-box score for selected items Motivation : Confidence Responses mHealth texting (weekly score 1 through 10)	Blending our foundational research on preventing hospitalizations, ^{38,39} with behavioral intervention theory, ¹¹³ our conceptual model suggests that decisions to seek care (behaviors) are influenced by capability (family capacity), opportunity (health system and susceptibility), and motivation (confidence). Confidence is a modifiable expression of self-efficacy to achieve an outcome, i.e., to avoid hospitalization and manage (respiratory) crisis at home.	A theorized mechanism of RE-PACT's effect is that the combination of action planning, mHealth surveillance, and coaching, will increase caregiver capability, opportunity, motivation to manage respiratory illness in severe CP.

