RCT participants in both groups will undergo assessments of demographic, clinical and caregiving measures reported through questionnaire and medical record review at baseline at 6 months after enrollment. Feasibility, acceptability and fidelity data will be collected through parent-report, medical record review, and research team logs monthly during the intervention, and, for control group participants, at 6 months after enrollment.

Data about research participants (children and their families) will be collected by study research assistants through electronic self-administered questionnaires or structured interviews with parents either over the phone or in person, abstraction of child medical record data by the study RAs, and (for intervention group families) through phone interactions and direct observation with health coaches in RE-PACT. Content of these assessments include parent-report questions about child and parent health, parent perceptions of child health, family socio-demographic information, care utilization, and experiences of caregiving.

Analyses will assess feasibility, acceptability, fidelity and effect size estimates (by comparing numbers of respiratory exacerbations between intervention and usual care groups). We will use pre-specified definitions of success for each of our feasibility, acceptability and fidelity measures. We anticipate being underpowered to assess the efficacy of the intervention in this pilot study, but to inform a future large RCT we will test differences between intervention and active groups in the primary and secondary clinical outcomes. For each of these measures, we will compare differences between intervention and active control group outcomes at 6 months controlling for their baselines. While we anticipate that the intervention and control groups will be similar due to random assignment, we will adjust for any variables in our analysis that are not equal between the groups given the small sample size. In addition, we will analyze for any effect of primary home language on the study outcomes, as this may affect families’ ability to navigate systems of care in the U.S. To explore theoretical intervention mechanisms, we will also test the mediating effect of caregiver capability, opportunity, and motivation measures on the relationship between intervention and respiratory illness outcomes.

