4.2 SCIENTIFIC RATIONALE FOR STUDY DESIGN

Rational for the study design. Conducting this pilot study will provide a high degree of certainty that the final RE-PACT protocol is feasible, acceptable and can be delivered with fidelity. This is a critical approach to designing interventions that can be integrated in diverse, real-world, settings and sustained.

Using an RCT design (i.e., with a control group who do not receive intervention) is necessary to establish effect sizes needed to adequately power an efficacy trial. The findings from this study will allow precise estimation of effect sizes to conduct a fully powered, multisite hybrid Type 2 effectiveness-implementation RCT.

Rationale for the type and selection of control conditions. The control group will be randomly assigned, allowing the study team to conclude that endpoint differences between each group are most likely due to the intervention itself.

Potential problems associated with the control group. The control group may have pre-existing respiratory action plans created during routine clinical care. In addition, the coach may have difficulty avoiding contaminating the control group by inadvertently conducting coaching activities to those not assigned to the intervention group. This risk will be minimized since action plans using the study protocol will only happen for intervention subjects, and coaching is triggered only through mHealth text responses and texting will only be set up for those assigned to the intervention.

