9.1 STATISTICAL HYPOTHESES

- Primary Feasibility, Acceptability, Fidelity Endpoint(s): RE-PACT's primary outcomes will be analyzed descriptively, and evaluate feasibility, acceptability, fidelity using multiple approaches. Each outcome will be

assessed against our pre-specified measures of success, e.g., achieving at least 80% enrollment. By conducting iterative refinements over three waves of implementation, we expect to achieve success in all measures. We will assess all participant feedback using both quantitative and qualitative data to determine what study design changes would enhance a large-scale RCT. We will use inductive content analysis of qualitative data.

- Secondary Efficacy Endpoint(s): **To inform a future large multisite RCT, we will test** differences between treatment (I or AC) groups in the primary and secondary respiratory illness outcomes. Our goal with these analyses is to estimate effect sizes for the differences between groups. The primary clinical outcome is severe respiratory illness rate, defined as the total number of severe respiratory illnesses divided by the person-months over the 6 months period. The severe respiratory illness rate will be analyzed with negative binomial (NB) regression models to account for overdispersion in the count data. In the primary analysis, univariate NB regression analysis will be conducted with study arm as a predictor variable. Study site will be a stratification factor to account for stratified randomization. The observed effect size of the analysis will be quantified in terms of relative risk (RR) and reported along with the corresponding 95% confidence interval. A generalized linear mixed effects model with a logit link function and subject specific random effects will evaluate **longitudinal changes** in the severe respiratory illnesses within and between study arms. An autoregressive (AR) correlation structure will account for within subject correlations. In this analysis, presence/absence of severe respiratory illness at the monthly assessments will be the dependent variable; study arm will be included as a predictor variable, and study site as a stratification variable to account for the stratified randomization. **To investigate theoretical mechanisms**, we will test the mediating effect of caregiver capability, opportunity, and motivation (COM-B)¹¹³ measures on the relationship between intervention and respiratory exacerbations.

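### Motivation is measured only in the intervention arm, so its planned regression on study arm and its Sobel mediation test cannot be computed

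*Combined protocol and SAP*

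**What the plan says.** Section 9.4.9 opens: "We will test the mediating effect of caregiver capability, opportunity, and motivation (COM-B) measures on the relationship between intervention and respiratory illness outcomes". It then sets out a sequence. The illness outcomes are compared between arms by negative binomial regression. The mediators come next, by "regressing each potential mediator variable (caregiver capability, opportunity, and COM-B) on the binary study arm variable". Where that association is significant, the outcome is regressed on mediator and arm. Last comes a Sobel z-test built from the two slopes. The parenthesis in the second step prints COM-B where the opening sentence has motivation.

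The same three mediators appear in the tertiary objective in Section 3 ("To explore the mediating relationships between RE-PACT and capability, opportunity, motivation (COM-B) measures"), in Section 4.1 ("we will also test the mediating effect of caregiver capability, opportunity, and motivation measures on the relationship between intervention and respiratory illness outcomes") and in Section 9.1 ("we will test the mediating effect of caregiver capability, opportunity, and motivation (COM-B").

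Motivation has a single measure in Section 3: "Confidence Responses mHealth texting (weekly score 1 through 10"). The measures table in Section 8.1 repeats it and gives its source as text logs, whereas capability (FCAT, GSES) and opportunity (FECC) come from surveys.

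On who is texted, the Schedule of Activities in Section 1.3 places text training and the weekly text under "Intervention Arm Only". Section 4.2 says "texting will only be set up for those assigned to the intervention". Section 6.3 gives the same restriction as a reason why blinding is impractical.

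**The concern.** A regression of a mediator on study arm needs values of that mediator in both arms. If motivation exists only in text logs, and only intervention families are texted, there is no control value to compare with. This is a failure of identification, not low power, and a larger sample would not cure it.

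Confidence is both the signal that triggers the just-in-time response and a theorized mechanism of the intervention, so readers will look for this result. Left as written, the plan leads at analysis either to an unexplained omission or to an improvised proxy. The gap cannot be filled once controls have left the study.

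**Working it through.** **Inputs**
- 90 participants allocated 1:1, hence 45 per arm; at most 10% missing, hence about 45 × 0.9 = 40.5 per arm (Sections 4.1 and 9.2).
- Motivation: text-log confidence score only (Sections 3 and 8.1).
- Texting: intervention arm only (Sections 1.3, 4.2 and 6.3).
- Controls: study assessments at baseline and exit (Sections 5.5 and 6.1.1). The survey measures listed in Section 8.1 are demographics, CGSQ, PHQ2, FCAT, GSES and FECC; none is the confidence item. The retention post cards and calls in Section 5.5 only update contact details.
- Multiple imputation: clinical outcomes only (Section 9.4.3).

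The documents give no sample size, power or effect figure for mediation, so there is no planned figure to reproduce. The check is whether the models can be fitted.

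**Step 2, motivation on arm.** M = a₀ + a·arm + e. The slope a is the intervention mean minus the control mean, and the control mean is taken over 0 records. The 45 usable records all have arm = 1, so the intercept and arm columns are identical. Every entry of X′X is 45, and its determinant is 45·45 − 45·45 = 0. The rank is 1 of 2, so a does not exist.

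**Step 3, outcome on arm and motivation.** Columns: intercept, arm, M. The first two are still identical, so the rank is 2 of 3. The motivation slope b can be estimated within the intervention arm; the arm effect adjusted for motivation cannot.

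**Sobel.** z = ab / √(b²·SE(a)² + a²·SE(b)²). With no a and no SE(a), z is undefined. Dropout does not change this. Imputation could not repair it even if extended to mediators, because no observed control value informs an arm difference.

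**If confidence were collected in both arms,** the ranks become 2 of 2 and 3 of 3. Illustrative power for the arm effect on confidence, two-sided 0.05, at assumed differences of 0.4 / 0.5 / 0.6 SD: 47.5 / 66.0 / 81.2% with 45 per arm and 43.2 / 60.9 / 76.5% with 40.

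**Secondary caveat: capability and opportunity.** These can be computed, but each has one post-randomization score, at exit (Section 8.1), when the 6-month event window closes (Section 9.4.3). Illness may therefore have moved the score. To size this, I simulated 5,000 trials per setting. Control events were negative binomial with mean 1 per year × 0.5 year = 0.5 and overdispersion 1.0 (Section 9.2). Exit score = arm shift − d × events + N(0,1), with no effect of score on illness. Steps 2 and 3 were linear, with Sobel at two-sided 0.05. Arm shift, d and rate ratio (intervention/control) are assumptions.

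Percentage of trials with a significant Sobel test:

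| Per arm | Rate ratio | Arm shift | d = 0 | d = 0.1 | d = 0.25 | d = 0.5 |
|---|---|---|---|---|---|---|
| 40 | 1 | 0.3 SD | 0.2 | 0.4 | 3.1 | 12.2 |
| 40 | 1 | 0.6 SD | 1.2 | 3.0 | 16.1 | 48.6 |
| 40 | 0.6 | 0.3 SD | 0.1 | 0.5 | 3.3 | 19.1 |
| 40 | 0.6 | 0.6 SD | 1.0 | 2.7 | 13.9 | 55.1 |
| 45 | 1 | 0.3 SD | 0.1 | 0.5 | 4.5 | 15.4 |
| 45 | 1 | 0.6 SD | 1.4 | 3.9 | 20.7 | 56.4 |
| 45 | 0.6 | 0.3 SD | 0.2 | 0.6 | 4.7 | 23.4 |
| 45 | 0.6 | 0.6 SD | 1.3 | 3.1 | 18.0 | 64.8 |

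If a significant arm effect on illness were also required first, which Section 9.4.9 does not state, the 40-per-arm figures fall to 0.0–0.6% at d = 0.1. At d = 0.5 they fall to 0.7–2.1% (rate ratio 1) and 7.1–14.8% (rate ratio 0.6).

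**The case against.** Several passages read as if everyone is texted. Section 4.1 has all participants consent to text surveillance, Sections 5.3 and 6.1.2 speak of participants or caregivers generally, and Section 7.3 defines loss to follow-up partly by failure to answer texts. These do not carry the point. Consent is given before allocation and is not delivery. The texting paragraph in Section 6.1.1 follows a sentence limited to those randomized to the intervention. Sections 1.3, 4.2 and 6.3 are explicit.

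The survey forms and the separate detailed SAP mentioned in Section 9.4.1 are not in the file, so a confidence item could exist there. That is fair as a limit on certainty: the supportable statement is that no control value is planned in these documents. The measures table, which sources motivation from text logs alone, makes a hidden item unlikely.

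The aim is exploratory, the pilot says it is underpowered for efficacy, and a model that cannot be fitted cannot produce a misleading motivation result. All true; this limits the importance of the point but does not make the analysis possible.

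The capability and opportunity caveat is weaker. Shared timing is a general limit of baseline-and-exit mediation designs. The simulated rates exceed 5% only at d = 0.25 with the larger arm shift, or at d = 0.5, and nothing in the documents shows that such values are likely. It therefore stands as a labelling matter only.

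**Conclusion.** The concern holds. With no control-arm confidence data planned (0 of 45), the arm slope and Sobel test for motivation cannot be estimated, so 1 of the 3 promised mediators is lost. This follows from the documents' own statements and needs no numerical assumption beyond the absence of an undisclosed confidence item in the control surveys.

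For capability and opportunity, the arm effect on the exit score is a valid randomized comparison. Only the score-to-illness slope, and hence the Sobel result, cannot be separated from illness changing the score; how much this matters depends on assumed effects.

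The plan should be corrected, although no primary or secondary result is affected.

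**What to change.** - In Section 9.4.9, and consistently in Sections 3, 4.1 and 9.1, remove motivation from the between-arm mediation analysis. State that text confidence will be analysed within the intervention arm only.
- For capability and opportunity, report the baseline-adjusted arm effect on the exit score as a randomized comparison. If the Sobel test is kept, label it and the score-to-outcome slope as exploratory association, not evidence of mediation.
- Correct COM-B in the second-step list of Section 9.4.9.

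These edits are a few sentences in four sections, need no new data, and can be made before the SAP is finalized (Section 9.4.1).

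Optional: add the 1–10 confidence item to the baseline and exit surveys that both arms already complete. This costs one question at two existing contacts and would allow a between-arm comparison of confidence. It would not establish mediation, because the item looks one month ahead (Section 6.1.1) and an exit rating comes after the event window. Before adding it, the sponsor must reconcile Section 2.3.2, under which low confidence is shared with the care team, with Section 4.2, which aims to avoid contaminating the control group.
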